7.1.4. Abnormal Laboratory Values

Any abnormality in a laboratory value that is new in onset or which has worsened in severity or frequency from the baseline condition and meets 1 of the following criteria will be recorded on the AE pages of the eCRF:

- Requires therapeutic intervention or diagnostic tests.
- Leads to discontinuation of investigational product.
- Has accompanying or inducing symptoms or signs.
- Is judged by the Investigator as clinically significant.

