7.1.5. Assessing Intensity and Relationship

All AEs will be assessed on 2 descriptive parameters: intensity and relationship to the investigational product:

- Intensity refers to the severity of an event and references impact on a subject's functioning.
- Relationship refers to the likelihood that the event being assessed was caused by the investigational product.

Intensity

Each AE will be classified according to the following criteria:

- Mild: The AE does not interfere in a significant manner with the subject's normal level of functioning.
- Moderate: The AE produces some impairment of functioning, but is not hazardous to the subject's health.

Severe: The AE produces significant impairment of functioning or incapacitation and is a definite hazard to the subject's health.

When changes in the intensity of an AE occur more frequently than once a day, the maximum intensity for the experience should be noted. If the intensity category changes over a number of days, those changes should be recorded separately (with distinct onset dates).

Relationship

Each AE will be assessed as to its relationship to the investigational product, based on the following criteria. Although the attribution by the Investigator will be collected for reported events, for analytic purposes a temporal association with the use of the investigational product will be assumed sufficient for at least plausible association.

Not related: No causal relationship exists between the investigational product and the AE, but an obvious alternative cause exists, e.g., the subject's underlying medical condition or concomitant therapy.

Possibly related: A connection with the administration of the investigational product appears unlikely, but cannot be ruled out with certainty. An AE may be considered possibly related if or when it meets 2 of the following criteria: (1) it follows a reasonable temporal sequence from administration of the investigational product; (2) it could not readily have been produced by the subject's clinical state, environmental or toxic factors, or other modes of therapy administered to the subject; or (3) it follows a known pattern of response to the investigational product.

Related: There is a reasonable/plausible possibility that the AE may have been caused by the investigational product.

When assessing the relationship to the investigational product, the following criteria will be considered:

- Positive rechallenge

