### **6.2.16 Early Termination Efficacy Assessments**

For analysis purposes, efficacy data collected from early termination (ET) visit will be assigned to the next scheduled visit.

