### **6.2.17 Unscheduled Visits**

In general, only scheduled post-baseline laboratory, ECG, and vital signs values will be tabulated. Post-baseline repeat/unscheduled assessments will be disregarded from table, although these post-baseline assessments will be listed in the relevant appendices to the CSR.

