### **Liver Function Parameter**

The number and percentage of subjects meeting certain liver function abnormality categories will be summarized by visit:

- Alanine Aminotransferase (ALT) assessment > 3 times upper limit of normal (ULN),

- Aspartate aminotransferase (AST) > 3xULN,
- ALT or AST: > 3xULN; > 10xULN; > 20xULN
- Total Bilirubin: > 1.5xULN; > 2xULN
- Alkaline Phosphatase: > 1.5xULN; >2xULN
- (ALT or AST > 3xULN) and total bilirubin>2xULN
- (ALT or AST>3xULN) and total bilirubin>2xULN and alkaline phosphatase<2xULN

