### Coagulation Parameter Abnormalities

- International Normalized Ratio (INR) >1.5

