### 6.13.4 Electrocardiogram Data

Descriptive statistics for observed values and changes from baseline in the following 12-lead ECG variables will be tabulated at each follow-up visit:

- Heart rate (beats/min)
- PR interval (msec)
- RR interval (msec)
- QRS complex (msec)
- QT interval (msec)
- QTc interval (msec)
- QTcF interval (msec) [Fridericia's formula - QTcF]

ECG Result Interpretation (Normal, Abnormal Not Clinically Significant [NCS], and Abnormal Clinically Significant [CS]) will be summarized by treatment group and visit.

The incidence of ECG abnormalities for subjects with any abnormal CS ECG result will be presented by treatment group and visit.

Additionally, the number and percentage of subjects in each treatment group who meet any of the following criteria for QT or QTcF will be tabulated by treatment group and visit.

- Maximum value >450 to 480 msec
- Maximum value >480 to 500 msec
- Maximum value >500 msec
- Maximum increase from baseline >30 to 60 msec
- Maximum increase from baseline >60 msec

Shift tables in relation to the overall interpretation (Normal, Abnormal NCS, and Abnormal CS) from baseline to each follow-up visit will be presented.

Box plots for ECG data will be provided for changes from baseline by visit and maximal change.

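### The by-arm liver table counts subjects only visit by visit and has no rows at the protocol's 5 and 8 × ULN stopping levels

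*SAP*

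**What the plan says.** SAP 6.2.17 sets a general rule that tables of post-baseline laboratory, ECG and vital-sign data use scheduled values: "Post-baseline repeat/unscheduled assessments will be disregarded from table". The omitted values go to listings.

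SAP 6.13.2, under Liver Function Parameter, says: "The number and percentage of subjects meeting certain liver function abnormality categories will be summarized by visit". The combined transaminase categories are "ALT or AST: > 3xULN; > 10xULN; > 20xULN". There are further categories for bilirubin, alkaline phosphatase, and ALT/AST above 3 × ULN with bilirubin above 2 × ULN. Under Coagulation Parameter Abnormalities the only entry is "International Normalized Ratio (INR) >1.5", not combined with ALT or AST. SAP Section 11 lists one table for these categories (14.3.4.7) and one subject-level listing (16.2.8.1.5).

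Protocol Section 4.3 makes discontinuation mandatory at several liver thresholds. Liver toxicity is the only toxicity for which it lists criteria. Protocol 7.1.4 makes a new or worsened laboratory abnormality an adverse event if, among other triggers, it "Leads to discontinuation of investigational product". Protocol 7.1.5 grades adverse events on function: "Intensity refers to the severity of an event and references impact" on the subject's functioning.

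**The concern.** The safety question between arms is how many subjects ever crossed each liver threshold. A by-visit table answers a different question: how many were above it at a given scheduled sample. Several cases spread over 24 weeks can then look like one or two per visit. The rows cannot be added exactly, because one subject can appear in more than one.

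The cutoffs add a second gap. A subject at 4 × ULN and one at 9 × ULN fall in the same rows of the table, although the protocol requires only the second to stop on enzyme level alone. The adverse event tables do not separate them, because intensity is not graded on multiples of ULN.

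The liver is a reasonable place to want a clear count. Protocol 3.2.1.2 reports transaminase rises in 10% to 15% of rheumatoid arthritis patients at 250 mg BID. Plasma levels there were 4 to 5 times those in the Phase 2a Alzheimer's studies, in which no liver test abnormality was seen. SAP Section 8 plans no DSMB analyses, so the final tables carry the comparison.

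**Working it through.** The plan gives no figure on this point to reproduce. The only design number used is 76 subjects per arm (Protocol 8.2, SAP 4).

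**Step 1. Stopping criteria against table rows.**

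| Protocol 4.3 criterion | Row in SAP 6.13.2? |
|---|---|
| ALT/AST > 8 × ULN | No; the levels are 3, 10 and 20 |
| ALT/AST > 5 × ULN for > 2 weeks | No |
| ALT/AST > 3 × ULN and bilirubin > 2 × ULN | Yes |
| ALT/AST > 3 × ULN and INR > 1.5 | No; INR stands alone |
| ALT/AST > 3 × ULN with symptoms or eosinophilia | No; cannot be shown by an enzyme cutoff alone |

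This comparison needs no assumption.

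**Step 2. What a by-visit display shows.** Assumptions, for illustration only: 8 of 76 subjects (8/76 = 10.5%) each have one episode above 3 × ULN lasting D days, with onset uniform over Days 0 to 168. The on-drug chemistry samples are at Days 21, 42, 84 and 126 (Table 6-1).

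- Chance of being abnormal at the sample on day p: min(p, D)/168.
- Chance of being abnormal at one or more samples: length of the union of the onset windows (p − D to p, cut at 0), divided by 168.

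| D | Mean chance per sample | Average row (× 8) | Chance at ≥ 1 sample | Different subjects (× 8) | Sum of the four rows |
|---|---|---|---|---|---|
| 14 | 14/168 = 0.0833 | 0.67 (0.9% of 76) | 56/168 = 0.333 | 2.67 (3.5%) | 2.67 |
| 28 | (21 + 3 × 28)/(4 × 168) = 0.1563 | 1.25 (1.6%) | 98/168 = 0.583 | 4.67 (6.1%) | 5.00 |
| 42 | (21 + 3 × 42)/(4 × 168) = 0.2188 | 1.75 (2.3%) | 126/168 = 0.750 | 6.00 (7.9%) | 7.00 |

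The ratio of different subjects to the average row is 4.0, 3.7 and 3.4 (0.333/0.0833, 0.583/0.1563, 0.750/0.2188). It does not depend on the assumed 8. Adding the rows overshoots by 0, 0.33 and 1.00 subject.

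**Step 3. Where repeat samples matter.** Scheduled on-drug samples after baseline are nominally 21, 42 and 42 days apart. Using the visit windows, the shortest gap is (42 − 3) − (21 + 3) = 15 days. A rise above 5 × ULN therefore cannot be rechecked at a scheduled treatment visit within two weeks. A prompt recheck would be a repeat or unscheduled sample, which the general rule keeps out of the table.

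**Step 4. Possible size of that exclusion.** The documents give no retest interval and no course for an enzyme rise, so this step is illustration only. It was simulated with 20,000 episodes in each of 8 scenarios: triangular rises lasting 30 to 63 days, peaks uniform on 3 to 12 × ULN, a retest every 3 or 7 days after a value above 3 × ULN, stopping by the > 8 × and > 5 × for > 2 weeks rules, an Early Termination (ET) panel within 3 days of stopping, and Follow-up at 14 ± 3 days.

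| Level reached | Seen only on unscheduled samples, ET panels tabulated | ET panels not tabulated |
|---|---|---|
| > 5 × ULN | 6–13% | 9–20% |
| > 8 × ULN | 3–8% | 28–50% |

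With all peaks fixed at 6, 7 or 8 × ULN and ET tabulated, the > 5 × figure ranges from 0 to 49%, so it depends heavily on the inputs. For > 3 × ULN it is 0% by construction, because the modelled retest always follows a scheduled value. Symptom-prompted tests are not modelled.

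**The case against.** The strongest reply is that little is hidden.

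- **Listings.** Listing 16.2.8.1.5 is devoted to liver and coagulation abnormalities. Listings sort by treatment group, so with about 76 per arm any-time counts could be made by hand. This stands as mitigation, but a hand count after the event is not a planned output.
- **Per-visit maxima.** The chemistry tables report the maximum by arm and visit, so a scheduled 9 × ULN value would show. They do not say how many subjects reached it.
- **Adverse events.** Protocol 7.1.4 also covers abnormalities that need intervention or diagnostic tests, or that are judged clinically significant. Many retested rises would be counted by arm at any time, though not by multiple of ULN.
- **Summing the rows.** In Step 2 this overshoots by at most one subject. That is fair: the loss in the illustration is small, but the sum remains an upper bound and not a count.
- **Room for exceptions.** The 6.2.17 rule is general, SAP Section 6 allows further tables in the study report, and the table shells are not in the documents, so an overall row cannot be ruled out. The text as written plans none.
- **No duty to mirror Section 4.3.** It governs subject management, and nothing requires the display to follow it. True, but its levels are the ones the trial acts on. The rows at 10 and 20 × ULN lie above the level at which dosing must already stop.
- **A sparse INR row.** Post-baseline coagulation is scheduled only at Day 84 and Follow-up, so a combined row from scheduled values would be nearly empty. That is a reason to include unscheduled values.

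A reader might infer that the SAP gives QT an any-time count and denies one to the liver, since 6.13.4 has categories such as "Maximum value >450 to 480 msec". The documents do not support this: those categories are also tabulated by visit.

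**Conclusion.** The point holds as a gap in the safety display, of minor to moderate importance. Followed as written, the SAP yields no per-arm count of subjects who crossed a liver cutoff at any time, and no count at three laboratory stopping criteria. Both conclusions rest on the text alone. The size in Step 2 depends on assumed episodes, and the percentages in Step 4 on an assumed retest schedule and enzyme course. Neither estimates what this trial will see.

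Three stronger readings are not supported. First, a reader might infer that liver data are lost or that subjects go unprotected. All values are listed, the stopping criteria apply during conduct, and abnormalities that lead to discontinuation are adverse events tabulated by arm. No efficacy result changes. Second, a reader might take the exclusion of unscheduled values as removing a known share of cases from the planned rows. The only non-zero losses computed are at 5 and 8 × ULN, which have no rows at present. The larger figures require that ET panels be left out. ET chemistry is a scheduled assessment, although SAP 6.2.16 says only that "efficacy data collected from early termination (ET) visit will be assigned to the next scheduled visit", and no rule places ET laboratory values in a by-visit table. Third, the blank Day 168 chemistry cell in Table 6-1 might be read as part of this defect. It concerns data collection, would need a protocol amendment, and is not relied on here.

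**What to change.** In SAP 6.13.2, as a stated exception to 6.2.17:

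1. Report, per arm, the number and percentage of subjects meeting each liver and INR threshold at any post-baseline time. Use scheduled, ET, repeat and unscheduled values, and keep the by-visit counts beside them.
2. Add rows for ALT or AST above 5 × ULN, above 8 × ULN, above 3 × ULN with INR above 1.5, and any Section 4.3 liver criterion met. Derive the two-week and symptom criteria as subject-level flags, not visit rows.
3. State where ET laboratory values fall in by-visit tables.

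The cost is two or three sentences and a few rows in Table 14.3.4.7, from data already collected and listed. The SAP's amendment table shows changes still being made before database lock in July 2019. A change made before lock is pre-specified; the same counts added later would have to be reported as additional analyses. The drawback is that any-time counts rise with the number of tests per subject, so an arm that is retested more can look worse. Keeping both displays lets the reader see this.

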### 6.2.18 Follow-Up Visit

A follow-up visit should be scheduled 14 (+/- 3) days after the last dose of study drug for all subjects that complete or are withdrawn from the study.

### 6.3 Conventions

All data listings, summaries, figures and statistical analyses will be generated using SAS version 9.3 or higher.

Summaries will be presented by treatment group or overall. Treatment group labels will be displayed as follows:

Neflamapimod  
(40 mg)

Placebo

*Overall columns are to be included within the table shells as follows:*

Demography	Treatment and overall
Baseline	Treatment and overall
Disposition	Treatment and overall
Efficacy	Treatment
PD	Treatment
PK	Treatment
AEs	Treatment
Other safety	Treatment

Listings will be sorted in the following order treatment group, subject, parameter, and visit unless otherwise stated. All data will be listed, subjects who were not randomized will be displayed after the randomized treatment groups.

Continuous variables will be summarized by the number of non-missing observations, mean, median, standard deviation, and minimum and maximum. For all tabulations of changes from baseline data, the lower and upper 95% confidence limits for the mean for the individual treatments will be given.

Categorical variables will be summarized by presenting the frequency and percent. Percentages will be based on the number of non-missing observations or the subject population unless otherwise specified. For each variable, all categories will be shown. Zero frequencies (but not the percent) within a category will be presented.

### 6.3.1 Decimal Places

Decimal places for derived data described in section 6.2 will be determined by the scale of measurement unless otherwise stated. No decimal places will be displayed if the smallest calculated value is  $\geq 100$ ; 1 decimal place will be displayed when the smallest value is within the interval (10, 100), with 10 being inclusive; 2 decimal places will be displayed when the smallest value is within (1, 10), with 1 being inclusive; and so on for even smaller scales of measurement.

Derived data where it is known in advance the result will be an integer for example *day, month, year, number of days and total scores (for rating scales)* will be presented with zero decimal places.

Means, medians and percentiles will be displayed to one more decimal place than the data, dispersion statistics (e.g. standard deviation) will have two more decimal places, and the minimum and maximum will be displayed to the same number of decimal places as reported in the raw data. Percentages will be displayed with one decimal place.

P- Values will be quoted to 3 decimal places. P-values  $< 0.001$  will be presented as  $p < 0.001$ . Where this value is less than 0.05, 0.01 or 0.001, attention will be drawn to this fact using the conventional “\*”, “\*\*” or “\*\*\*” annotation, respectively.

## 6.4 Subject Disposition

Subject disposition will be summarized as follows:

- The number of subjects, who entered in the study, were randomized and are in each population will be summarized by treatment group and overall for Enrolled Subjects.
- The number of subjects who failed screening and the reasons for failure will be tabulated for Enrolled Subjects.
- The number of study completers, early withdrawals and the reasons for withdrawals will be tabulated by treatment group and overall for the Safety and Efficacy Analysis Population.

## 6.5 Protocol Deviations

Separate tabulations of previous and ongoing conditions at screening will be presented by treatment group and overall for the Safety Population. Conditions will be presented by Medical Dictionary of Regulated Activities (MedDRA version 21.0) primary system organ class and preferred term.

## 6.8 Prior and Concomitant Medications

Separate tabulations will be produced for prior and concomitant medications presented by treatment group and overall for the Safety Population. Prior medications are defined as all medications starting before the date of first dose of study drug. Concomitant medications are defined as medications taken on or after the date of first dose of study drug. Concomitant medications will be summarized by Anatomical Therapeutic Chemical (ATC) level 2 and Preferred Name using the World Health Organization (WHO) dictionary (Version WHODrug Global B3 March 2018). In addition, CNS medications will be summarized similarly.

## 6.9 Exposure to Study Drug and Treatment Compliance

Extent of exposure will be presented by randomized treatment group for the Safety Population (see [Section 6.1.1](#)).

Overall compliance (%) will be calculated as: [Total number of capsules dispensed minus total number capsules returned, divided by the expected number of tablets (based on the number of days from first dose to last dose)] multiplied by 100, as a percentage.

Number and percentage of subjects who had at least 80% of the (cumulative) planned dose will be summarized by treatment group. In addition, the number (%) of subjects with compliance within each of the following intervals will be provided:

- 95 - 100%
- 90 - <95%
- 85 - <90%
- 80 - <85%
- 75 - <80%
- 70 - <75%
- <70%

## 6.10 Efficacy Analyses

All efficacy analyses will be based on the Evaluable Efficacy Population by randomized treatment regardless of the treatment actually received. Descriptive statistics by treatment group

and visit will be reported for all efficacy endpoints. All statistical tests will be performed using a two-tailed 5% overall significance level, unless otherwise stated. All comparisons between treatments will be reported with 95% confidence intervals for the difference.

There will be no imputation of missing efficacy data.

### 6.10.1 Primary Endpoint

The primary efficacy endpoint is:

Combined change in z-scores of total recall and delayed recall on the HVLT-R in neflamapimod-treated subjects compared to placebo-recipients at Week 24.

Neflamapimod 40 mg group will be compared to the placebo group.

The hypothesis test is as follows:

H0:  $\mu_{\text{neflamapimod}} = \mu_{\text{placebo}}$

H1:  $\mu_{\text{neflamapimod}} \neq \mu_{\text{placebo}}$

The null hypothesis will be rejected at a significance level of  $\alpha$  (two-sided) = 0.05. There will be no p-value adjustment for multiplicity.

### 6.10.2 Primary Efficacy Analysis

The primary endpoint will be analyzed using Mixed Model for Repeated Measures (MMRM) with fixed effects for treatment, background AD-specific therapy (cholinesterase inhibitor or memantine versus no cholinesterase inhibitor or memantine), CDR-Global Score of 0.5 versus 1.0, scheduled visit (nominal) and scheduled visit by treatment interaction, random effect for subject and baseline z-score as a covariate. Least-square means (LSM) and 2-sided 95% confidence intervals (CI) will be provided for treatment group differences and estimated endpoint values by visit.

The normally-distributed assumption for the combined change in z-scores of total recall and delayed recall on the HVLT-R will be examined (at 0.05 alpha level). In case the assumption is violated, rank transformed data will be applied to the MMRM model. Ranks will be determined separately within each time point, based on observed data only.

In addition, Scale plot will be provided for combined change in z-scores of total recall and delayed recall on the HVLT-R at each post-baseline visit by treatment group.

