Following completion of informed consent procedures, subjects will enter the Screening phase of the study.

Two Screening visits are planned to allow most screening procedures to be completed and reviewed during the first visit before lumbar puncture to collect CSF is performed during Screening Visit 2.

Once eligibility is confirmed and before the first dose of study drug, subjects will be randomly assigned on 1:1 basis to placebo or neflamapimod treatment. Investigators and subjects will be blinded to the treatment assignment.

Dosing will start on Day 1 following completion of all Baseline procedures.

During the treatment period, subjects will return to the clinic on Days 21, 42, 84, 126, and 168. Telephone contacts will be conducted to determine subject status and assess compliance between Days 42 and 84 (Visits 5 and 6); Days 84 to 126 (Visits 6 and 7); and Days 126 and 168 (Visits 7 and 8).

Episodic memory and other cognitive assessments will be performed at Baseline and Days 42, 84, and 168.

Lumbar puncture will be performed, and CSF collected at Screening Visit 2 and on Day 168.

A Follow-up visit will be conducted 14 (± 3) days following the last dose of study drug.

TABLE OF CONTENTS

SPONSOR PROTOCOL APPROVAL PAGE	2
INVESTIGATOR’S SIGNATURE OF AGREEMENT PAGE	3
SPONSOR CONTACT INFORMATION	4
SYNOPSIS	5
TABLE OF CONTENTS	9
LIST OF TABLES	12
LIST OF ABBREVIATIONS	13
1. INTRODUCTION	15
1.1. Scientific Rationale	15
1.2. Pre-Clinical Pharmacology Results	16
1.3. Prior Clinical Experience	16
2. OBJECTIVES	20
2.1. Primary Objective	20
2.2. Secondary Objectives	20
3. INVESTIGATIONAL PLAN	21
3.1. Overall Study Design and Plan	21
3.1.1. Screening.....	21
3.1.2. Treatment Period	21
3.1.3. Follow Up.....	21
3.1.4. Early Discontinuation.....	21
3.2. Discussion of Study Design	21
3.2.1. Rationale for Dose Selection	22
4. SELECTION OF STUDY POPULATION	24
4.1. Inclusion Criteria	24
4.2. Exclusion Criteria	24
4.3. Removal of Subjects from Treatment	25
5. TREATMENTS ADMINISTERED	27
5.1. Packaging and Labeling	27
5.2. Study Drug Supply, Storage, and Handling	27
5.3. Drug Accountability, Disposal, Return, or Retention of Unused Study Drug	27
5.4. Method of Assigning Subjects to Treatment Group	28
5.5. Study Blinding and Breaking the Blind	28

5.6.	Dose Modification for Toxicity	28
5.7.	Prior and Concomitant Therapy	28
5.8.	Contraception and Pregnancy	30
5.9.	Activity Restrictions	31
5.10.	Treatment Compliance.....	31
6.	STUDY ASSESSMENTS AND PROCEDURES	32

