6.2.6. Mini-Mental State Examination/CDR

The MMSE (Folstein et al, 1975) consists of 11 tests of orientation, memory (recent and immediate), concentration, language, and praxis. Scores range from 0 to 30, with lower scores indicating greater cognitive impairment. It is based on the performance of the subject and takes approximately 5 to 10 minutes to administer.

The CDR (Hughes, 1982) is a semi-structured interview resulting in a semi-quantitative scoring of cognitive impairment in milder and more progressed forms of dementia. It is sensitive in both AD dementia and Mild Cognitive Impairment (MCI), and is an approved regulatory endpoint recognized by the FDA. The CDR interview is to be conducted with the subject and Caregiver by an experienced and certified clinician. The CDR yields both a global and an SB score. The global CDR rating, along with the memory box score, will be used to determine a subject's eligibility for inclusion. In addition, the CDR-SB score will be utilized to evaluate cognitive and functional changes from baseline to Visit 6 and Visit 8.

Standardized MMSE (Version 2.0) and CDR will be conducted by the Investigator or designee.

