### 6.10.3 Sensitivity Analyses

- Repeat the primary efficacy analysis with the Per Protocol Population
- Use an analysis of covariance (ANCOVA) with treatment group, background AD-specific therapy, CDR-Global Score as main effects and the baseline z-score as the covariate to compare Z-scores of total recall and delayed recall on the HVL T-R at Week 24 in the neflamapimod and placebo groups

The results of the ANCOVA will be summarized using the treatment groups' least square means, the difference between the treatment groups' least square means, the 95% confidence interval for the treatment group difference and the p-value.

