#### 6.10.4 Secondary Analyses

The secondary efficacy endpoints at Week 24 and follow-up when applicable are:

- Change in WMS immediate and delayed recall composites in neflamapimod-treated subjects compared to placebo-recipients.
- Change in CDR-SB in neflamapimod-treated subjects compared to placebo-recipients.
- Change in MMSE in neflamapimod-treated subjects compared to placebo-recipients.
- Change in CSF biomarkers (T-tau, P-tau181, A $\beta$ 1-40, A $\beta$ 1-42, neurogranin, neurofilament light chain) in neflamapimod-treated subjects compared to placebo-recipients at the end of treatment.

The same method used for the primary efficacy analysis will be applied for the analyses of the change in WMS and change in CDR-SB.

Changes in MMSE and CSF biomarkers will be compared using an analysis of covariance (ANCOVA) with treatment group, background AD-specific therapy, CDR-Global Score as main effects and the baseline assessment as the covariate. The results of the ANCOVA will be summarized using the treatment groups' least square means, the difference between the treatment groups' least square means, the 95% confidence interval for the treatment group difference and the p-value. Scale Plots of Mini-Mental State Examination (MMSE) Score by Visit and by Treatment; and Baseline and Change from Baseline to Day 84 MMSE Score.

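### The primary MMRM names only a subject random effect; fitted as written, its Week 24 standard error uses a variance averaged over three visits

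*SAP*

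**What the plan says.** SAP 6.10.2 calls the primary model a mixed model for repeated measures. Its fixed effects are treatment, background AD therapy and CDR-Global Score, and the description ends with "scheduled visit (nominal) and scheduled visit by treatment interaction, random effect for subject and baseline z-score as a covariate". If a normality check at the 0.05 level fails, the same model is run on ranks: "Ranks will be determined separately within each time point, based on observed data only".

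The hypothesis in SAP 6.10.1 concerns "neflamapimod-treated subjects compared to placebo-recipients at Week 24" only. On the error rate, SAP 6.10 says: "All statistical tests will be performed using a two-tailed 5% overall significance level, unless otherwise stated". The HVLT-R schedule is in the protocol synopsis and Table 6-1: "Episodic memory and other cognitive assessments will be performed at Baseline and Days 42, 84, and 168". The model therefore has three post-baseline visits.

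SAP 6.10.3 adds a Week 24 sensitivity analysis: "Use an analysis of covariance (ANCOVA) with treatment group, background AD-specific therapy, CDR-Global Score as main effects and the baseline z-score as the covariate". SAP 6.10.4 extends the primary model: "The same method used for the primary efficacy analysis will be applied for the analyses of the change in WMS and change in CDR-SB". Protocol 6.2.6 says "the CDR-SB score will be utilized to evaluate cognitive and functional changes from baseline to Visit 6 and Visit 8", that is, Days 84 and 168.

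Protocol 8.5.1 leaves the specific analyses to the SAP. Neither document states a residual covariance structure, an estimation method, degrees of freedom, a robust variance or a rule for non-convergence.

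**The concern.** A subject random intercept with independent residuals implies one variance at every visit and one correlation between every pair of visits. The model then estimates that variance from all three visits and applies it to the Week 24 contrast. The resulting standard error is right only if the Week 24 variance equals the average, and nothing in the documents supports that for a change score measured at 6, 12 and 24 weeks.

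What is at stake is the stated 5% level and the 95% interval of the primary test. If spread grows towards Week 24, the standard error is too small and the test too liberal. If spread shrinks, power is lost. WMS and CDR-SB inherit the same model.

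**Working it through.** **Inputs from the documents.** 76 subjects per arm, 1:1 allocation, two-sided 5%, effect sizes 0.46 and 0.53 (SAP 4, 5, 6.10); post-baseline visits on Days 42, 84 and 168; primary contrast at Week 24. **Assumed:** the relative SDs at each visit, because the documents give none.

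**1. The plan's own power.** Power = Φ(ES × √(76/2) − 1.96).
- ES 0.46: 0.46 × 6.164 = 2.84, and Φ(2.84 − 1.96) = 80.9%.
- ES 0.53: 0.53 × 6.164 = 3.27, and Φ(3.27 − 1.96) = 90.4%.

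With the noncentral t the figures are 80.4% and 90.1%. The stated 80% and 90% reproduce.

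**2. Effect of the averaged variance, complete data.** The random-intercept model estimates the total variance as the mean of the three visit variances. Hence

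SE ratio = √[mean(v42, v84, v168) / v168], and true two-sided error = 2 × [1 − Φ(1.96 × ratio)].

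For 0.8/0.9/1: (0.64 + 0.81 + 1)/3 = 0.817; √0.817 = 0.904; 1.96 × 0.904 = 1.771; error = 7.7%. The correct standard error is √(2/76) = 0.162 in Week 24 SD units; the model reports 0.147, and the nominal 95% interval covers about 92%.

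| Relative SD, Days 42/84/168 (assumed) | SE ratio | Type I error |
|---|---|---|
| 1/1/1 | 1.000 | 5.0% |
| 0.95/0.975/1 | 0.975 | 5.6% |
| 0.9/0.95/1 | 0.951 | 6.2% |
| 0.8/0.9/1 | 0.904 | 7.7% |
| 0.7/0.8/1 | 0.843 | 9.9% |
| 1.25/1.1/1 | 1.121 | 2.8% |

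In the last row, power at ES 0.46 falls from 81% to Φ(2.84 − 1.96 × 1.121) = 74%.

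**3. CDR-SB, two visits (Days 84/168).** 0.9/1 gives ratio 0.951 and 6.2%; 0.8/1 gives 0.906 and 7.6%; 1.25/1 gives 1.132 and 2.7%.

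**4. Simulation with dropout.** 76 per arm, correlation 0.5, 5% lost after Day 42 and 8% after Day 84 completely at random, REML fits, 20,000 null runs per pattern (Monte Carlo error 0.15 to 0.2 points).

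| Relative SD (assumed) | Random intercept |
|---|---|
| 1/1/1 | 5.0% |
| 0.9/0.95/1 | 6.5% |
| 0.8/0.9/1 | 7.8% |
| 0.7/0.8/1 | 10.1% |
| 1.25/1.1/1 | 2.6% |

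The unstructured model gave 4.9% to 5.3% in all five patterns. Power (6,000 runs per pattern), unstructured against random intercept, was 76.3% against 76.7% with equal SDs, and 76% against 69% with falling SDs.

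The simulation used treatment-by-visit cell means without the baseline or stratification covariates, and t references with 280 and 130 df instead of Kenward-Roger.

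A separate, smaller simulation at 0.8/0.9/1, with other correlations and 0% or 15% dropout, gave 7.2% to 8.2% for the random intercept. It gave 5.3% to 6.8% for the unstructured model, but on 400 runs each (Monte Carlo error about 1.1 points).

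**The case against.** The strongest reply is that this is an omission, not an error. The label MMRM is often read as implying an unstructured covariance, and the text does not say that the residuals are independent. That is fair, and it is why the conclusion is conditional on the model being fitted as written. But the SAP names a random effect instead of a covariance structure, so a programmer could defensibly code either model for the one test on which the trial rests.

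Second, the harm has no documentary basis, and the larger figures need strong assumptions. Suppose spread grew only through linear individual slopes at weeks 6, 12 and 24. A Day 42/168 SD ratio r then needs slope differences to make up (16/15)(1 − r²) of the Week 24 variance: about 10% for r = 0.95, 20% for 0.9, 38% for 0.8 and 54% for 0.7. This stands as a caution: the milder rising patterns, 5.6% to 6.2%, are easier to defend than 7.7% or 9.9%.

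Third, other planned outputs would expose or reduce the problem. The Week 24 ANCOVA uses only Week 24 variance and is tabulated for both the Efficacy and Per-Protocol populations. SDs will be reported by visit. Ranking within visits largely equalises the variances. All true, but the ANCOVA and the SDs do not change the primary p-value, and the ranks apply only if normality is rejected.

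Fourth, SAP 6.10.7 treats the secondary endpoints as descriptive. So for WMS and CDR-SB the issue is interval coverage, not a confirmatory error rate.

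Finally, the simulation is simpler than the SAP model and does not test Kenward-Roger. The closed form gives the same pattern without it.

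**Conclusion.** The concern holds. As written, the primary model's Week 24 standard error is valid only if the Week 24 variance equals the average over Days 42, 84 and 168. For the assumed patterns shown, true two-sided error runs from 2.8% to 9.9% with complete data; a gentle rise in spread gives about 6%. Direction and size cannot be known from the documents, and with constant spread there is no error. The averaging is exact with complete data and approximate with dropout. This is a recommended correction, to be made before unblinding so that the covariance is not chosen with the results in view.

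**What to change.** In SAP 6.10.2, replace the subject random effect with an unstructured within-subject covariance across Days 42, 84 and 168, fitted by REML with Kenward-Roger degrees of freedom. State the order to follow if it does not converge: heterogeneous Toeplitz, then compound symmetry with a sandwich variance. Name the degrees of freedom for that last step too. Other fallback orders are defensible; what matters is that one is fixed in advance.

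In SAP 6.10.4, use an unstructured covariance over each endpoint's own scheduled visits: Days 42, 84 and 168 for WMS, and Days 84 and 168 for CDR-SB. Use each endpoint's own baseline as covariate.

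A separate point for the same edit: SAP 6.2.16 moves early-termination data to the next scheduled visit. It should be clear that this means the next visit with that test, since Table 6-1 has no HVLT-R, WMS or CDR on Day 126.

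The cost is SAP wording and a few lines of code. HVLT-R and WMS have six covariance parameters instead of two, and CDR-SB three instead of two. With equal SDs the simulated power loss was 76.7% to 76.3%, within Monte Carlo error.
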